11.1.1.2. Reporting Adverse Events

AEs, whether spontaneously reported by the subject or noted by authorized study personnel, will be recorded in the subject's medical record and on the appropriate AE eCRF. Each recorded AE will be described by its duration (i.e., start and end dates), severity, regulatory seriousness criteria if applicable, suspected relationship to the DE-122, actions taken and outcome.

AEs that occur after any subject has provided written informed consent, before treatment, during treatment, or within 30 days following the cessation of treatment, whether or not they are related to the study, must be recorded. To improve the quality and precision of acquired AE data, Clinical Investigators should observe the following guidelines:

- Whenever possible, use recognized medical terms when recording. Do not use colloquialisms and/or abbreviations.
- If known, record the diagnosis (i.e., disease or syndrome) rather than component signs and symptoms and /or laboratory or test findings (e.g., record congestive heart failure rather than dyspnea, rales, and cyanosis, and enlarged heart on chest x-ray). However, other events that are considered unrelated to an encountered syndrome or disease should be recorded as individual AEs (e.g., if congestive heart failure and severe headache are observed at the same time and are clinically unrelated, each event should be recorded as an individual AE).
- If the diagnosis is not known, then record the leading component sign, symptom or test finding and describe the other clinically related findings in the narrative description of the case. A suspected diagnosis can be used and described as such (e.g., record suspected or probable myocardial infarction); this has to be updated in the clinical database once the diagnosis is confirmed.

AEs occurring secondary to other events (e.g., sequelae) should be identified by the primary cause. A primary AE, if clearly identifiable, generally represents the most accurate clinical term. If a primary AE is recorded, events occurring secondary to the primary event should be described in the narrative description of the case. For example:

The subject developed orthostatic hypotension and subsequently fainted and fell to the floor wherein she experienced a head trauma and neck pain.

The primary AE in this example is orthostatic hypotension. The fall, head trauma and neck pain should be described in the narrative description of the case.

- For intermittent events (e.g., intermittent headache), the event onset date should be recorded as the date the subject first started to experience the event and resolution date should reflect when the last occurrence resolved or stopped. Separate AEs for each event should not be recorded. For example, if a subject experienced headache on 14SEP2015 lasting for three hours, then subsequently experienced intermittent episodes of headache every day for approximately 3 hours until 21SEP2015, then the AE date of onset is 14SEP2015 and the resolution date is 21SEP2015.
- For intermittent events, record the maximum severity of the individual events. For example, if a subject complains of intermittent headaches for one week and the severity of each headache ranges from mild to moderate, then the severity would be moderate.
- For intermittent hospitalizations occurring for a primary AE (e.g., in a subject with multiple sclerosis, commonly known for its relapsing and remitting course, in some cases leading to multiple hospital confinements), the subsequent hospitalizations should be described in the narrative description of the case.
- If treatment was initiated, include the treatment and duration of the medication(s) in the eCRF.

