7.4. Dose Adjustment Criteria

The Safety Review Team will review safety parameters after the first subject in a given cohort has completed Visit 3 (Day 8±1). The remaining subjects in the cohort will receive the same dose if neither the safety criteria for adjusting or stopping doses ([Section 7.4.1](#)) nor the criteria for study termination ([Section 7.5](#)) preclude their treatment.

When the first 2 or 3 subjects in Cohort 1 and 3 subjects in other Cohorts have completed Visit 5 (Day 30±2), the Safety Review Team will again evaluate the safety parameters. If the safety criteria for adjusting or stopping doses and the criteria for study termination are not met, the first subject in the next cohort will receive the next higher DE-122 dose level.

The same safety evaluations will be performed for each cohort.

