7.4.1. Safety Criteria for Adjusting or Stopping Doses

If more than one of the following dose limiting toxicities is observed in any one cohort, planned doses may be adjusted or stopped by the Safety Review Team.

- Visual acuity loss from baseline defined as:
 - Loss of best corrected visual acuity (BCVA) of 30 or more letters not due to vitreous hemorrhage or injection procedure **OR**
 - Transition to no light perception (NLP) not due to injection procedure
- Clinically significant inflammation defined as:
 - > 3+ vitreous haze as measured by the National Eye Institute Grading Scheme ([Nussenblatt et al., 1985](#)) **OR**
 - Sterile endophthalmitis (including the presence of hypopyon)
- Severe IOP elevation as measured by tonometry, on two separate exams, at least one day apart, excluding day of injection (despite pharmaceutical intervention):
 - > 35 mmHg **OR**
 - Increase of > 15 mmHg from baseline

If any of the following adverse events (AEs) occur in any one subject in any cohort, planned doses will be adjusted by treating additional subjects at the same or lower dose level (the occurrence of a second adverse event in either the same or different subjects in one cohort will qualify for study termination, [Section 7.5](#)):

- Retinal non-perfusion of the study eye/vascular occlusion
- Vasculitis
- Retinitis
- > 2+ disc edema
- > 2 quadrants of retinal hemorrhage

If there is insufficient safety information in a given cohort at any time, the Safety Review Team may determine to treat additional subjects within that cohort before moving to the next cohort.

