7.5. Criteria for Study Termination

Unacceptable safety signals that prevent moving to the next higher dose cohort or result in stopping the study may include any of the following, if deemed to be related to study drug DE-122 (not DE-122 administration procedures):

- Pattern of systemic AEs
- Any of the following AEs in any 2 subjects in any cohort:
 - Retinal Non-perfusion of the study eye/vascular occlusion
 - Vasculitis
 - Retinitis
 - > 2+ disc edema
 - > 2 quadrants of retinal hemorrhage

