14.1.1. Study Endpoints

Safety:

- Incidence and severity of adverse events (AEs), slit-lamp biomicroscopy, indirect ophthalmoscopy, BCVA, IOP, fundus photography, fluorescein angiography, serum chemistry, hematology, urinalysis, vital signs, physical exam, EKG and pregnancy

Bioactivity:

- Change in CST and macular volume based on SD-OCT at each visit post DE-122 treatment

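### Protocol 11.1.1.2 puts events secondary to a recorded AE in the narrative only, with no exception for the events that 7.4.1 and 7.5 count

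*Protocol*

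**What the plan says.** Protocol 11.1.1.2 (Reporting Adverse Events) asks sites to record the primary event and adds: "If a primary AE is recorded, events occurring secondary to the primary event should be described in the narrative description of the case". Its worked example keeps orthostatic hypotension as the AE and moves the fall, head trauma and neck pain to the narrative. Events that are clinically unrelated are treated differently: "each event should be recorded as an individual AE". No class of event is exempted from the sequela rule.

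Protocol 7.4.1 lists five findings: retinal non-perfusion or vascular occlusion, vasculitis, retinitis, disc edema above 2+, and retinal hemorrhage in more than 2 quadrants. One occurrence in any subject leads to dose adjustment, and "the occurrence of a second adverse event in either the same or different subjects in one cohort will qualify for study termination". Protocol 7.5, which 7.4.1 cites for termination, uses the same five findings but words the count differently: "Any of the following AEs in any 2 subjects in any cohort". It also limits the criterion to events judged related to DE-122 and not to the administration procedure.

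SAP 8.1 tabulates subjects by system organ class and preferred term, each subject once at maximum severity. SAP 4.3.1.3 classes an AE as ocular from the location entered on its AE record.

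**The concern.** The recording rule and the counting rule work on different units. Section 7.4.1 counts a second listed event even in the same eye, whereas 11.1.1.2 gives a second event no record of its own if it follows from the first. The form then lacks the fields that the later rules need. Section 7.5 turns on relatedness, and Protocol 11.1.1.1 and 11.1.1.2 attach relatedness, onset and severity to AEs that are recorded. A narrative-only event need not carry any of these.

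Safety is the primary objective, and incidence and severity of AEs is the first-listed endpoint in Protocol 14.1.1. Escalation is decided on 2 or 3 subjects in Cohort 1 and 3 in each later cohort. At that size one unrecorded event can be the whole signal for its term.

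**Working it through.** **Plan's own figures.** The plan gives no event rate, power or alpha here. Its only related figure is the total of about 12, which agrees with the cohort sizes: 2 + 9 = 11 or 3 + 9 = 12.

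**Step 1: effect on the AE table.** The SAP 8.1 counting rule was applied to hypothetical records.

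| Case in one subject | Each event recorded | Sequela in narrative only |
|---|---|---|
| Vasculitis, then occlusion | vasculitis 1, occlusion 1, any ocular AE 1 | vasculitis 1, occlusion 0, any ocular AE 1 |
| Non-ocular AE, then ocular sequela | ocular term 1, any ocular AE 1 | ocular term 0, any ocular AE 0 |
| Two post-injection episodes of one term | 1 subject at maximum severity | not a sequela; merged record gives 1 subject at maximum severity |

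The loss is one subject for the sequela's term, together with its severity if that was the higher of the two. The any-ocular count changes only in the second case. Merging episodes changes nothing.

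**Step 2: effect on the 7.4.1 count.** With vasculitis and then occlusion in one subject, two listed events have occurred and one AE record exists. The different-subject count can fail too. Suppose subject A has vasculitis, and subject B has sterile endophthalmitis (not among the five) followed by vasculitis. The AE form shows listed events in one subject instead of two, under both 7.4.1 and 7.5.

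**Step 3: possible size.** The documents give no rates, so these are assumptions: p is the chance that a subject has a listed event, and q the chance that such a subject also has a second listed event as a sequela. Subjects are independent, and each affected subject's first listed event is recorded. With n subjects and X ~ Binomial(n, p):

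- visible on AE records: V = P(X ≥ 2)
- two-event rule met: M = V + q × P(X = 1)

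For n = 3, p = 0.10: V = 3 × 0.10² × 0.90 + 0.10³ = 0.028, and P(X = 1) = 3 × 0.10 × 0.90² = 0.243. With q = 0.25, M = 0.028 + 0.25 × 0.243 = 0.089.

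| n | p | V | M, q = 0 | M, q = 0.10 | M, q = 0.25 | M, q = 0.50 |
|---|---|---|---|---|---|---|
| 3 | 0.10 | 0.028 | 0.028 | 0.052 | 0.089 | 0.150 |
| 3 | 0.20 | 0.104 | 0.104 | 0.142 | 0.200 | 0.296 |
| 2 | 0.10 | 0.010 | 0.010 | 0.028 | 0.055 | 0.100 |

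The gap M − V is zero when q = 0. It concerns AE records alone and is smaller where the sequela is bleeding, which has its own report.

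**Step 4: the two counting rules.** Two listed events in one subject satisfy the second-event wording of 7.4.1 however they are recorded. They do not satisfy the two-subject wording of 7.5. Better recording does not remove this contradiction.

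**The case against.** The strongest reply is that 7.4.1 is not tied to the AE form. Protocol 7.4 says: "The Safety Review Team will review safety parameters after the first subject in a given cohort has completed Visit 3". Under Protocol 11.2 those parameters include ophthalmoscopy, BCVA, IOP, fundus photography and angiography. Ophthalmoscopy is done at every visit with abnormalities described, the sequela is still in the narrative, and about 12 subjects can be read one by one. This stands in large part, and the Team may well see the event. It does not fully replace an AE record. Ophthalmoscopy grades retina, macula and choroid only as normal or abnormal, in eyes that enter with active exudative disease. After screening, photography and angiography are scheduled only at Days 30, 60 and 90, so neither informs the Day 8 review. SAP section 8 specifies no summary of either. None of these sources supplies relatedness.

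It is also fair that 11.1.1.2 is a guideline that applies where a primary event is clearly identifiable, so a lost record is possible and not certain. Retinal hemorrhage is largely protected: ocular bleeding is an event of special interest under Protocol 11.1.3, reportable within 24 hours and listed under SAP 8.1.

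A reader might infer two further problems that the documents do not support:

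- **Recurrences.** The sentence "Separate AEs for each event should not be recorded" concerns intermittent events, illustrated by a week of daily headaches. It does not say that an ocular event which resolves and returns after a later injection is merged. Where post-injection episodes are merged, "For intermittent events, record the maximum severity of the individual events" applies, and SAP 8.1 counts the subject once at that maximum, so the table is unchanged.
- **IOP.** No passage makes an IOP rise narrative-only. Protocol 11.2.6 specifically requires the 10 mmHg rise to be reported as an AE, and SAP 8.4 lists subjects with such an increase from baseline. What remains is a general rule that does not say it gives way to the specific one.

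**Conclusion.** The point holds for sequelae. A listed event judged secondary to another AE can lack its own onset, severity and relatedness. Its preferred term then reads 0 instead of 1 subject in a cohort of 2 or 3, and the second-event count in 7.4.1 can be missed on the AE form. The size per affected subject is one lost term. The frequency is unknown, and the probabilities above rest on assumed p and q.

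It would go too far to say that the form cannot show second events or that ocular toxicity is under-counted across the board. Listed events in different subjects, and unrelated events in one subject, get their own records unless the listed event is itself a sequela. The any-ocular count usually stays right. Neither document names a primary AE table; AEs are one of several measures under the primary objective. This is an inexpensive improvement to safety recording. Separately, the counting units of 7.4.1 and 7.5 contradict each other.

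**What to change.** Add an exception to Protocol 11.1.1.2: every event named in 7.4.1 or 7.5, and every event of special interest, is recorded as its own AE with onset, severity and relationship to DE-122 and to the injection procedure, and is linked to the primary AE when judged secondary to it. The narrative rule stays for all other secondary events. Add that the IOP rise defined in 11.2.6 follows that section's AE-reporting rule even when secondary. Repeat both in the eCRF completion guidelines.

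The sponsor must also reconcile 7.4.1, which counts events in the same or different subjects, with 7.5, which counts subjects. This review does not say which should govern, and the recording fix changes no threshold.

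The cost is a short protocol addition, a note to sites and a few extra AE lines per affected subject. The downside is that related terms from one causal chain will appear together in the tables; the link to the primary AE lets a reader see this.

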11.1.2. Serious Adverse Events

SAEs are defined as any findings that suggest a significant hazard, contraindication, side effect, or precaution. Any adverse event is considered a serious adverse event if it results in any of the following outcomes:

- Death
- Life threatening:

A life-threatening event is any event that places the subject at immediate risk of death from the event as it occurred; it does not refer to an event that hypothetically might have caused death if it were more severe.

- Hospitalization, at the minimum an overnight stay
- A persistent or significant disability/incapacity
- A congenital anomaly/birth defect

- Other medically significant events:
Other medically significant events are events that may not result in death, be life-threatening, or require hospitalization but may be considered a serious adverse drug experience when, based upon appropriate medical judgment, they may jeopardize the subject and may require medical or surgical intervention to prevent one of the outcomes listed above.
- Sight threatening event:
A sight-threatening event is any event that places the subject at immediate risk of permanently losing vision in either eye as a direct result of the event.

11.1.2.1. Reporting Serious Adverse Events

A SAE eCRF must be completed with as much information available within 24 hours of knowledge of the event.

To improve the quality and precision of acquired SAE data, Clinical Investigators should observe the following guidelines:

- **Death** - Death is an outcome of an event. The event that resulted in the death should be recorded and reported as a SAE.
- **Hospitalizations for Surgical or Diagnostic Procedures** - The illness leading to the surgical or diagnostic procedure should be recorded as the SAE, not the procedure itself. The procedure should be captured in the case narrative as part of the action taken in response to the illness.

When new significant information (including the outcome of the event) is obtained, the Clinical Investigator should enter the information directly into the eCRF within 24 hours or as soon as possible after knowledge of the information.

Depending on the nature and seriousness of the AE, Santen may request additional documentation, for example, copies of the ophthalmic and medical record of the subject as well as results of laboratory tests. If the subject was hospitalized, the site should summarize the hospital discharge summary and provide to Santen upon request.

11.1.2.2. Expedited Reporting of Serious Adverse Events

Santen (or designee) will provide the Principal Investigator with a reporting cover letter and an anonymized MedWatch 3500A for expedited reporting of SAEs to the IRB or IEC. The Principal Investigator is responsible for receiving and reviewing expedited safety reports, submitting expedited safety reports to the IRB or IEC, and maintaining copies of expedited safety reports in the study records.

11.1.3. Events of Special Interest

Events of Special Interest (ESIs) are events that may require special attention for the purposes of on-going patient safety review during this study. The following are considered ESIs and should be reported on the appropriate eCRF with as much information as available within 24 hours of knowledge of the event:

- **Study medication administration error** – Study medication administration errors determined to be significant by the Clinical Investigator will be reported and evaluated as ESIs. Examples of study medication administration errors may include, but are not limited to: overdose of study medication and administration of study medication from an incorrect kit.
- **Pregnancy** - There are no controlled data with the investigational product in human pregnancy. It is required that women of childbearing potential use effective contraception during the study and recommended for 12 weeks after the completion of the study. Any pregnancy occurring during study treatment should be reported and the subject removed from the study. The subject should be followed until the end of pregnancy or until the end of the study, whichever is longer.
- **Ocular telangiectasia and bleeding** – There is no data showing that the investigational product is related to these events. However, these are seen in the Osler-Weber-Rendu (OWR) syndrome, a genetic condition that causes endoglin dysfunction. DE-122 binds to and suppresses human endoglin, thus information about the ocular manifestations of OWR are of value in predicting possible ocular adverse following IVT injection of DE-122. Any ocular telangiectasia or bleeding (both extra and intraocular) occurring during study treatment should be reported and the subject followed until the end of the study or resolution of the event.

11.1.4. Follow-up of Adverse Events

All reported AEs at study exit will be followed by the Clinical Investigator (or his/her designee) until the event is resolved or determined to be irreversible, chronic, or stable.

In addition, on a case-by-case basis, Santen (or designee) may request follow up beyond the end of the study.

If the Santen Pharmacovigilance Department requests follow-up on an individual SAE or designated ESI, site response to follow-up requests should be faxed to Santen Pharmacovigilance: [contact] (fax) or [contact].

11.1.5. Manual Back-Up Reporting Procedures

This study is utilizing an electronic data capture (EDC) system for data collection. In the event that the EDC system is unavailable for electronic reporting, the manual back-up reporting procedures below should be followed.

- Complete an AE and SAE form.
- Attach a fax cover sheet with your contact information and address to Santen Pharmacovigilance.
- Fax the cover sheet and the AE and SAE form to Santen Pharmacovigilance at [REDACTED]

When the EDC system becomes available, update the EDC system with all previously reported information.

11.2. Safety Parameters

The safety assessments will include adverse events (AEs), BCVA, slit-lamp biomicroscopy, indirect ophthalmoscopy, intraocular pressure (IOP), serum chemistry, hematology, urinalysis, vital signs, physical exam, fundus photography, fluorescein angiography, EKG, pregnancy.

11.2.1. Physical Examination

A full body systematic physical exam will be conducted by the Clinical Investigator or an external internist during Screening (Day -7 to Day -1) and Visit 8/Exit (Day 90±3).

11.2.2. Electrocardiogram (EKG)

EKGs will be performed at Screening (Day -7 to Day -1), Visit 3 (Day 8±1), Visit 5 (Day 30±2) and at Visit 8/Exit (Day 90±3). The Clinical Investigator will review the EKG report for abnormalities.

11.2.3. Vital Signs

Blood pressure and heart rate will be measured at each visit using an automated or manual blood pressure monitor. Systolic and diastolic blood pressures will be recorded in millimeters of mercury (mmHg), and heart rate will be recorded in beats per minute (bpm).

11.2.4. Best Corrected Visual Acuity

The BCVA will be recorded using the ETDRS chart and total number of letters at 4 meters and 1 meter will be recorded at each visit. If a subject could not read ETDRS chart, Finger Counts, Hand Motion, Light Perception, or No Light Perception will be recorded.

11.2.5. Slit-lamp Biomicroscopy

Slit-lamp biomicroscopy will be performed at each visit. On the visit of DE-122 or anti-VEGF injection, a biomicroscopy examination will be performed prior to DE-122 or anti-VEGF injection and a second one within 30 minutes after injection.

11.2.6. Intraocular Pressure

IOP will be measured by applanation tonometry and reported in millimeters of mercury (mmHg) at each study visit. On the visit of DE-122 or anti-VEGF injection, IOP will be measured before DE-122 or anti-VEGF injection and 40 (±10) minutes after injection. If post-injection IOP is increased ≥ 10 mmHg from pre-injection IOP, the IOP will be measured again 60 (±10) minutes following injection. If there is an increase of ≥ 10 mmHg at 60 (±10) minutes post-injection compared to pre-injection IOP, the subject will be prescribed a topical IOP-lowering medication until he or she returns for follow-up per the Clinical Investigator's discretion (an unscheduled visit may apply), and the IOP increase of ≥ 10 mmHg shall be reported as an AE.

